## **3.2.** Interim statistical analysis

In this study, no interim data analysis is planned.

# **3.3.** Planned number of participants in a clinical trial study based on the sample size

This open-label MD NOLTREXTM safety assessment study includes eligible and non-eligible patients who received MD NOLTREXTM as part of the IA/PAAG-SI/OA/2019 study. Therefore, no formal calculation of the sample size was performed. The maximum expected number of study participants is the number of patients who were randomized to the MD NOLTREXTM group in the IA/PAAG-SI/OA/2019 study, i.e. 72 patients.

## 3.4. Applicable level of significance

Statistical analysis of all the presented efficacy and safety parameters will be carried out at a 5% significance level, using two-way versions of statistical criteria.

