#### 3.1.2. Analysis of safety parameters

In this study, the main parameters are safety parameters:

- 1. The frequency of AE and/or SAE;
- 2. Overall assessment of the tolerability of therapy by the investigator and the patient;
- 3. The main parameters of vital activity (heart rate, blood PRESSURE, body temperature, BDD);
- 4. Results of physical examination of the knee joint;
- 5. Results of laboratory and instrumental examination.

In addition, it is planned to evaluate the cumulative (in the framework of a double-blind and open study) frequency of the most likely complications associated with periprocedural or temporary postprocedural (no more than 72 hours) pain or burning.

Other possible side effects and complications of special interest related to the method of intra-articular injection will also be presented separately:

- pain or swelling at the injection site, feeling of bursting, burning, arthralgia, effusion in the joint, synovitis, aseptic acute arthritis;
- infections (pyogenic arthritis, direct infection of the joint at infectious diseases, osteomyelitis, sepsis, etc.);
- subcutaneous neuropathies, drug-induced vascular embolism.

It is planned to analyze the safety parameters for all included patients (safety population or FAS) using descriptive statistics, as well as in the following subgroups:

- those who received only one course of injections in the placebo-controlled study IA/PAAG-SI/OA/2019;
- those who received two courses of therapy both in the placebo-controlled and at Visit 1 (and as per the indications at Visit 2) of the open study;
- those who received two courses of therapy both in the placebo-controlled and at Visit 3 (and as per the indications at Visit 4) of the open study.

For comparison between these subgroups, variance analysis (for quantitative parameters) or the "Chisquare" criterion (for qualitative parameters) will be applied, followed by the application of multiple comparison criteria (if necessary).

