#### **3.1.3.** Analysis of efficacy parameters

Main efficacy parameters of the studied MD:

1. Change in the overall score on the WOMAC scale (WOMAC-T) on Visit 3 (week 13), Visit 5 (week 25) compared to the basal value on Visit 0 (screening) of the open study and compared to the basal value on Visit 1 (week 1) of the IA/PAAG-SI/OA/2019 study;

2. Change in the pain subscale score (WOMAC-A) on Visit 3 (week 13), Visit 5 (week 25) compared to the basal value on Visit 0 (screening) of the open study and compared to the basal value on Visit 1 (week 1) of the IA/PAAG-SI/OA/2019 study;

3. Change in the score for stiffness subscale (WOMAC-B) and functional performance (WOMAC-C) at Visit 3 (week 13), Visit 5 (week 25) compared to the basal value at Visit 0 (screening) of open study and compared to the basal value at Visit 1 (week 1) of the study IA/PAAG-SI/OA/2019;

4. The change in the severity of pain in the target knee on a 100-mm VAS at Visit 2 (week 1), Visit 3 (week 13), Visit 5 (week 25) compared to the basal value at Visit 0 (screening) of open safety study and compared to the basal value at Visit 1 (week 1) study IA/PAAG-SI/OA/2019;

5. Evaluation of the effectiveness of treatment by the patient, parameter OEP (on a scale from 1-clear deterioration to 6-significant improvement) on Visits 3 and 5 (parameters OEP-w13 and OEP-w25, respectively);

6. Evaluation of the effectiveness of treatment by the investigator, parameter OEI (on a scale from 1-clear deterioration to 6-significant improvement) on Visits 3 and 5 (parameters OEI-w13, OEI-w25, respectively);

7. Assessment of the total number of paracetamol tablets taken (one tablet = 500 mg) starting from day 1 on Visits 3 and 5 (PARACETAMOL -w13 and PARACETAMOL-w25, respectively);

8. Assessment of the total number of NSAID tablets taken starting from day 1 on Visits 3 and 5 (NSAID-w13 and NSAID-w25, respectively);

9. The parameter JSN of the target knee joint at Visit 5 of the open study compared to the basal value on Visit 0 of the IA/PAAG-SI/OA/2019 study retrospectively.

All performance parameters will be analyzed both among all patients included in open study no. IA/PAAG-SI/OA/2020 (using descriptive statistics) and in subgroups of patients:

- those who received only one course of injections in the placebo-controlled study IA/PAAG-SI/OA/2019;
- those who received two courses of therapy both in the placebo-controlled and at Visit 1 (and as per the indications at Visit 2) of the open study;

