- those who received two courses of therapy both in the placebo-controlled and at Visit 3
  (and as per the indications at Visit 4) of the open study.

For comparison between these subgroups, variance analysis will be used (for quantitative parameters other than those based on WOMAC), covariance analysis (for quantitative parameters based on WOMAC, in this case the initial value of WOMAC in the double-blind phase of the study will be used as a covariate, and the results will be presented as the average, calculated by the least squares method), or the "Chi-square" criterion (for qualitative parameters), followed by the application of multiple comparison criteria (if necessary).

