## 3.8. Selection of study participants for analysis

Due to the fact that the main purpose of this study is to analyze safety parameters, the main population for the analysis of all studied parameters of efficacy and safety will be the safety population, which is defined as the population of all patients included in the study (due to the fact that all included patients were exposed to the studied medical device), which most corresponds to the full data set for analysis (Full Analysis Set, FAS).

Additionally, performance data will also be analyzed in a population that strictly conforms to the study Protocol, known as the Per Protocol – PP data set.

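### All between-subgroup comparisons are tested at 5% with none primary, in subgroups formed largely by pain response: a significant difference would not be evidence on single versus repeated courses

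*SAP*

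**What the plan says.** SAP 3.4 sets one rule for everything: "Statistical analysis of all the presented efficacy and safety parameters will be carried out at a 5% significance level". All tests are to be two-sided.

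SAP 3.1.3 lists nine numbered items under the title "Main efficacy parameters of the studied MD". None is called primary and there is no order of testing; the protocol's list of effectiveness parameters does not rank them either. Most items contain several comparisons. The first reads "Change in the overall score on the WOMAC scale (WOMAC-T) on Visit 3 (week 13), Visit 5 (week 25"), and each of these changes is taken from two baselines: "compared to the basal value on Visit 0 (screening) of the open study and compared to the basal value on Visit 1 (week 1"), where the second belongs to the 2019 study.

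The whole group is described without tests. The three treatment-course subgroups (no further course, a second course from Visit 1, a second course from Visit 3) are compared by analysis of variance, analysis of covariance or chi-square, "followed by the application of multiple comparison criteria (if necessary"). SAP 3.1.2 uses the same tests and the same optional step for safety.

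SAP 3.8 adds a second analysis set for efficacy: "Additionally, performance data will also be analyzed in a population that strictly conforms to the study Protocol". SAP 3.1.2 also sets the priority: "In this study, the main parameters are safety parameters".

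**The concern.** A 5% level limits false positives for one test. Here it is applied separately to many tests, with nothing stating which of them would support a conclusion. The optional multiple-comparison step follows the three-group test, so it deals with which pairs of subgroups differ on one parameter. It does not deal with the number of parameters, visits and baselines. The between-subgroup tests are nowhere labelled exploratory, so any parameter that falls below 0.05 could be reported as a significant difference on a main parameter.

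A second problem makes such a result harder still to interpret. The subgroups were not allocated. SAP 3.6 says that they follow actual need for treatment, and the protocol's Research method section ties that need mainly to whether pain fell by 40% from Visit 1 of the 2019 study. A comparison of pain-related scores between them partly measures the rule that formed them.

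**Working it through.** **1. Count of comparisons (SAP 3.1.3).** Each is one three-group test.

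| Parameter | Visits × baselines | Listed | Testable between subgroups |
|---|---|---|---|
| WOMAC-T | 2 × 2 | 4 | 4 |
| WOMAC-A | 2 × 2 | 4 | 4 |
| WOMAC-B and WOMAC-C | 2 scales × 2 × 2 | 8 | 8 |
| VAS pain | 3 × 2 | 6 | 4 |
| OEP | 2 visits | 2 | 2 |
| OEI | 2 visits | 2 | 2 |
| Paracetamol | 2 visits | 2 | 2 |
| NSAID | 2 visits | 2 | 2 |
| JSN | 1 | 1 | 1 |
| Total | | 31 | 29 |

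VAS at Visit 2 loses its two comparisons because the protocol restricts Visit 2 to patients injected at Visit 1, so only one subgroup has data. The count leaves out the Per Protocol repeat and all safety comparisons.

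**2. Error if there is no true difference.** The plan states no familywise error rate, so there is no figure to reproduce beyond 5% per test.

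- Expected number of p<0.05: 29 × 0.05 = 1.45, whatever the correlation.
- Chance of at least one, if independent: 1 − 0.95^29 = 0.774.

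The parameters are not independent, and the documents give no correlations. They were therefore assumed and varied: 29 equally correlated normal outcomes, one-way F tests, 72 patients split 24/24/24 or 40/22/10 (also assumed), 4,000 runs per setting.

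| Assumed correlation | 24/24/24 | 40/22/10 |
|---|---|---|
| 0 | 77% | 76% |
| 0.3 | 66% | 65% |
| 0.5 | 52% | 51% |
| 0.7 | 35% | 36% |
| 0.8 | 27% | 27% |
| 0.9 | 18% | 18% |
| 0.95 | 13% | 13% |

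Other simulation runs of the same kind put the figure at 0.9 at about 17%. The subgroup split hardly matters; the correlation does.

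A model closer to the actual structure was also run: four scales, two shared baselines, WOMAC-T as a weighted sum of its subscales, other outcomes linked to VAS change, and JSN unrelated. It gave 44% to 67%, with assumed correlations of 0.3 to 0.9 between scales and 0.3 to 0.6 over time. All these runs use one-way F tests, a simplification of the planned mix of methods.

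**3. Effect of how the subgroups form.** The no-difference case in step 2 is hypothetical. Under the protocol's Research method section:

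- Patients whose pain fell by less than 40% from Visit 1 of the 2019 study are re-injected at Visit 1 (Group A).
- Those with a fall of 40% or more, or who cannot be re-injected, are not (Group B).
- Group B is reassessed at Visit 3 against the same 40% rule.

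Group A therefore enters with more residual pain relative to its 2019 value, and the two parts of Group B are separated by pain at Visit 3. VAS and WOMAC will differ between subgroups even if re-injection does nothing.

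The size was examined by simulating 72 patients with no injection effect, subgroups formed by the 40% VAS rule, and the SAP's analysis of covariance of WOMAC-T change to Visit 5 with the double-blind baseline as covariate. Assumptions: correlation over time 0.3 to 0.7, VAS–WOMAC correlation 0.5 to 0.7, and assumed means and standard deviations. That one test gave p<0.05 in about 33% to 78% of runs with the Visit 0 baseline, and about 12% to 40% with the 2019 Visit 1 baseline. A separate simulation under similar assumptions gave 36% to 73% and 11% to 46%. The nominal rate is 5%.

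**The case against.** The best defence is that this is an open, single-group safety study. Whole-group efficacy is descriptive, there is no sample size calculation, and no hypothesis or success criterion is attached to any subgroup p-value. The Per Protocol set is additional; SAP 3.8 makes the safety population the main one. On this view the tests are plainly exploratory, and multiplicity control would be out of proportion.

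Much of that stands. No confirmatory conclusion is at risk, and formal adjustment is not what the plan needs. But the plan does not say that the subgroup tests are exploratory; it says the opposite in form, by setting a significance level for every parameter. SAP 3.1 refers to a fuller description in the statistical analysis plan, and the documents supplied contain nothing further that fills the gap.

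A reader might infer three stronger things that the documents do not support:

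- **That a false positive is likely.** At the low end of the range it is not. The 77% needs independence, which is impossible when WOMAC-T contains its subscales and follow-up scores are reused against two baselines. Nor is there a firm lower limit, since 13% is reached at 0.95.
- **That the Per Protocol repeat doubles the problem.** It reuses the same patients and is additional, so it cannot be counted as 29 fresh tests.
- **That naming one primary comparison, such as WOMAC-T at Visit 5, would solve it.** That phrase still covers two baselines, and step 3 of the working shows that one such test would not hold 5% as a test of repeat injection.

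**Conclusion.** The point holds for the secondary, between-subgroup comparisons. The count of 29, the absence of a primary parameter and the lack of control across parameters come straight from the documents. The chance of at least one p<0.05 under no difference, roughly one in six to three in four for correlations from 0.9 down to 0, rests on assumed correlations and subgroup sizes. It exceeds 5% at every value tried.

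The formation of subgroups by pain response is the more serious limit, because no multiplicity correction removes it. Its direction follows from the protocol's own rule; the percentages in step 3 depend on assumed correlations, means and standard deviations and are illustrative only.

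The descriptive safety results and the whole-group efficacy description are not called into question.

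**What to change.** In SAP 3.4, 3.1.2 and 3.1.3, replace the blanket 5% rule for between-subgroup comparisons with a statement to this effect:

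- All comparisons between the three treatment-course subgroups, for efficacy and safety and in both the FAS and the Per Protocol set, are exploratory.
- They are reported as differences with 95% confidence intervals.
- Any p-values are descriptive and unadjusted. The open-ended multiple-comparison step is removed.
- Subgroups were formed by need for treatment, so no claim about single versus repeated courses rests on these comparisons.

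Do not keep one comparison as a confirmatory 5% test. Bonferroni adjustment (0.05/29 = 0.0017 per test, familywise error 4.9% if independent) would address the number of tests but not the selection, so it is not a substitute.

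The cost is SAP wording only: no new data, visits or patients. The downside is that the sponsor gives up claims of statistical significance between subgroups.

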## 3.5. Criteria for termination of the study

The study can be stopped for the following reasons:

1. at the initiative of the sponsor:

a. obtaining new toxicological or pharmacological data, or data on SAE, which force to revise the previously conducted assessment of the benefits/risks of participation in the study;

b. the frequency of AE and/or their severity does not allow to continue the study;

c. other reasons, including administrative.

2. at the initiative of the investigator: the frequency of AE and/or their severity unacceptably increases the risk for patients participating in the study

3. by decision of regulatory authorities.

If the study is stopped early, the Sponsor is obliged to notify the personnel of the research centers, as well as the regulatory bodies, indicating the reason for the early termination of the study.

The rules for terminating the research for each research participant are listed in Section Ошибка! Источник ссылки не найден.

## **3.6.** Procedures to count the missing, non-analyzable, and questionable data

During the monitoring visits to the clinical center, the monitoring specialists authorized by the sponsor will conduct an analysis of patient's eCRF to identify any lack of necessary data. In the absence of data in the eCRF and the availability of relevant information in the primary documentation, the questions to the investigators and instructions for eliminating the inconsistencies will be formulated.

The statistician, authorized by the sponsor, and the principal investigator, when checking the database of research results, will analyze for the presence of dubious, missing and non-analyzable data, and will also formulate questions for investigators.

Researchers, if possible, will eliminate the identified errors in eCRF and inform the main researcher and authorized representatives of the sponsor about this. If the detected errors in the data cannot be eliminated after the completion of patient participation in the study, the statistical analysis of the data will be used to analyze the sensitivity of the resulting parameters to the doubtful data found. Information about the missing, doubtful and non-analyzable data will be presented in the final clinical trial report.

For all parameters of efficacy, safety and tolerability, data recovery is not provided due to the fact that the distribution of patients into subgroups for analysis is based on the actual need for treatment, and is not based on any procedures for distribution into groups, so the missing values cannot be considered as missing accidentally or completely accidentally.

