### 3. Description of statistical methods

#### **3.1.** Description of statistical methods to be used

Statistical analysis will be carried out using specialized software, the selection of which will be carried out during the preparation of the statistical analysis plan.

Continuous (quantitative) data will be presented using the number of observations, arithmetic mean, 95% confidence interval (CI) for mean, standard (mean-square) deviation, median, interquartile range (25th and 75th centile), minimum and maximum.

Qualitative data (ordinal, nominal) will be presented using absolute frequencies (number of observations), relative frequencies (percent) and 95% CI.

Unless otherwise specified in the statistical analysis plan, statistical tests will be two-sided with a 5% confidence level.

The medical history and AEs will be encoded using the MedDRA classifier in the current version. Concomitant and prior therapy will be encoded using the ATX classifier.

This section briefly describes the planned analysis. The full analysis will be described in the statistical analysis plan.

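### As posted, efficacy is in effect an observed-case analysis that assigns premature-end data no use, and analgesic need is a raw tablet total rather than use per observed day

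*SAP*

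**What the plan says.** SAP 3.6 rules out imputation for all efficacy, safety and tolerability parameters: "data recovery is not provided due to the fact that the distribution of patients into subgroups for analysis is based on the actual need" to be treated. It concludes: "so the missing values cannot be considered as missing accidentally or completely accidentally". Where data errors cannot be corrected after a patient has finished, the statistical analysis "will be used to analyze the sensitivity of the resulting parameters to the doubtful data found". On reporting, it says: "Information about the missing, doubtful and non-analyzable data will be presented in the final clinical trial report".

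SAP 3.1.3 defines the WOMAC changes and the patient and investigator effectiveness ratings (OEP, OEI) at Visits 3 and 5, and VAS pain at Visits 2, 3 and 5. WOMAC and VAS changes are taken from two baselines: Visit 0 of the open study and Visit 1 of the parent study. The analgesic parameters are "Assessment of the total number of paracetamol tablets taken (one tablet = 500 mg) starting from day 1 on Visits 3 and 5" and "Assessment of the total number of NSAID tablets taken starting from day 1 on Visits 3 and 5". Whole-group efficacy is descriptive. Subgroups are compared by analysis of variance, by analysis of covariance for WOMAC, or by chi-square.

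The protocol's list for the visit that ends participation early includes WOMAC, VAS, OEP, OEI and both tablet totals. Reasons for withdrawal must be documented (Protocol, Exclusion criteria).

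SAP 3.1 calls itself brief and adds: "The full analysis will be described in the statistical analysis plan".

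**The concern.** Declining to impute is not neutral. With no imputation, a mean or an analysis of variance at a fixed visit uses only patients who have a score at that visit. That approach leans heavily on ignorable missingness, which SAP 3.6 has just denied. Calling the population FAS (SAP 3.8) does not supply absent scores, and the per-protocol set is not a missing-data analysis.

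Leaving may be related to outcome. Under the telephone-contact rule, analgesic use on five or more days in each of two weeks running brings an invitation to either an unscheduled or a premature-end visit. Exclusion criterion f covers patients who receive or need additional treatment that could affect the results.

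The tablet total has its own difficulty. It grows with time observed, so a heavy user who leaves early can look like a light user who stays.

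Knee function and analgesic need form the second stated task of the study. SAP 1.1.2 cites tablet counts as objective measures, and there is no concurrent efficacy control against which a selective loss would show.

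**Working it through.** The plan gives no figure to reproduce: 72 is an enrolment ceiling, no sample-size calculation was done (SAP 3.3), and no dropout rate is stated. Leaver numbers, gaps and use rates below are assumptions.

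**1. VAS, whole group.** Let k of 72 patients be absent at a visit, with improvement D mm worse than that of patients present. Then overstatement of mean improvement = (k/72) × D.

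| k | D = 0 | D = 10 mm | D = 30 mm |
|---|---|---|---|
| 4 | 0 | 0.6 | 1.7 |
| 7 | 0 | 1.0 | 2.9 |
| 14 | 0 | 1.9 | 5.8 |

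Patients who leave after Visit 3 still contribute there. If 7 of 14 leavers do so, the bias is 1.0 to 2.9 mm at week 13 and 1.9 to 5.8 mm at week 25.

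**2. Paracetamol.** Visit 1 is Day 1 and Visit 5 is Day 169, so full follow-up is 168 days or 24 weeks. Assume a completer takes 4 tablets a week: 4 × 24 = 96 tablets, and 96/168 = 0.571 per day. Assume a leaver takes 8 a week: 8/7 = 1.143 per day. Let 14 of 72 be leavers.

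| Exit day | Leaver's total | Raw mean, (14 × total + 58 × 96)/72 | Raw mean/168 | Total use/total observed days |
|---|---|---|---|---|
| 42 | 48 | 86.7 | 0.516 | 0.604 |
| 84 | 96 | 96.0 | 0.571 | 0.633 |
| 126 | 144 | 105.3 | 0.627 | 0.659 |

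Pooled denominators are 14 × exit day + 58 × 168, that is 10,332, 10,920 and 11,508 days.

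The mean of patient-level rates is (14 × 1.143 + 58 × 0.571)/72 = 0.683 at every exit day. Omitting leavers gives 0.571.

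Against 0.683, omission understates use by about 16% (1 − 0.571/0.683). Raw totals understate it by about 24%, 16% and 8% for exit at day 42, 84 and 126. A Day-84 leaver at twice the daily rate has exactly a completer's total.

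The ±2-day visit windows move a completer's total by only about 2.4% at Visit 3 (2/84) and 1.2% at Visit 5 (2/169), so the problem lies with leavers.

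**3. NSAID unit.** The permitted products include one taken once daily and others taken twice daily (Protocol, Prohibited concomitant therapy, item 5). At those amounts, 96 days of use is 96 tablets of the first kind or 96 × 2 = 192 of the second. This arises even without dropout and can distort a comparison in either direction.

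**The case against.** Declining to impute when data are not missing at random is defensible. Whole-group efficacy is descriptive, safety is the main purpose, missing data will be described in the report, and the posted text defers detail to a fuller plan. All of that stands, and it lowers the priority. It does not supply a sensitivity analysis for leavers or a rule for partial tablet totals.

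Three stronger readings are tempting, and the documents do not support them.

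- A reader might infer that premature-end scores are discarded. The text is silent: it assigns them no use, and the fuller plan may do so.
- A reader might infer that leavers are expressly shut out of the sensitivity analysis. The data review in SAP 3.6 does cover missing data. Only the sensitivity sentence is confined to doubtful data, so leavers are not clearly covered.
- A reader might infer that heavy analgesic use forces exit. Neither document says so; an unscheduled visit is an equal alternative.

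The direction of bias in subgroup comparisons is also not fixed. It depends on which subgroup loses patients. At week 13, the subgroup injected at Visit 3 has lost nobody by construction, since membership requires attending that visit.

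**Conclusion.** The point holds for the posted text. SAP 3.6 calls the missing values non-random and then leaves an analysis of whoever is present, with no stated use for exit data already being collected. If leavers do worse, whole-group improvement is overstated. Under the assumed losses and gaps this is 0.6 to 5.8 mm on the VAS, and it is zero if leavers do no worse. The actual size cannot be known from the documents.

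The tablet totals are the firmer part, because the definition is stated rather than left open. Partial and full-period totals are not comparable, and use is understated when leavers have the higher daily rate, whether they are omitted or entered raw. The figures of 8% to 24% depend on 14 leavers at twice the completers' rate.

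None of this bears on the collection or reporting of data, or on the safety analysis. It is an improvement the sponsor should make, at modest priority, unless a fuller plan already covers it.

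**What to change.** Keep the observed-case analysis as the main one.

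1. **SAP 3.1.3.** Report paracetamol and NSAID tablets per observed diary day for each patient, including leavers up to exit. Use this patient-level rate in the subgroup comparison alongside the raw total. A rate per patient fits the planned analysis of variance; a pooled group ratio does not. Show NSAIDs by product, or as days of use if diary entries are dated.
2. **SAP 3.6.** Add two sensitivity analyses in the FAS.
   - (a) Carry premature-end WOMAC, VAS, OEP and OEI to every later efficacy visit: Visit 3 if it was not reached, and Visit 5.
   - (b) For leavers whose documented reason is target-joint pain, lack of effect or a target-joint adverse event, credit no improvement. For each of the two baselines separately, take the worse of zero change and the observed exit change in WOMAC and VAS. For example, take VAS of 60 at parent Visit 1, 36 at Visit 0 and 50 at exit. Against Visit 0 the observed +14 is kept. Against parent Visit 1 the observed −10 becomes 0.

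The cost is SAP wording and a few extra tables. Exit scores, tablet counts and withdrawal reasons are already collected. The documents do not confirm that NSAID product or dated entries are recorded with each count. The figures may be less favourable, and rates for very early leavers will be noisy. Analysis (a) rests on a carry-forward assumption and (b) on a judgement in coding reasons, so neither should replace the main analysis. No clinical rule changes.
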